To ensure concealment, the primary investigator, assessors and administrators of the randomisation were blinded to the block sizes, as the randomisation code was stored in REDCap, with no access for the project group.

Sample size and power considerations

The sample size and power estimation were based on the expected between-group difference in the change in SPADI score from baseline to the 12 weeks follow-up. In order to achieve an *a priori* statistical power of at least 85%, with a two-sided significance level $\alpha=0.05$, with an anticipated standard deviation (SD)=15.41 SPADI units (5), the estimated total sample size was n=130 (~ 65 participants in each group), to be able to detect a minimal clinically relevant difference defined as 8 points on the SPADI-score (6,7).

[figure not shown]
Correction:

In the study protocol we estimated an eligible population of approximately n=384 women willing to participate (<https://doi.org/10.1186/s13063-022-06659-1>), based on the cross sectional survey sent to

Individualised treatment vs. a home-based exercise program in women with late-term shoulder impairments after primary breast cancer surgery

approximately 4.300 women in Region of Southern Denmark, corresponding to an expected eligible population rate of 8%.

In fact, we sent out the questionnaire to 9.934 women nationwide, and obtained a participation rate of 56.7% in the cross sectional survey. For the Region of Southern Denmark we received 1.164 complete replies. Of these only 129 women matched the inclusion and exclusion criteria, and furthermore, 76% of these eligible women declined the offer to participate, resulting in $n=31$, corresponding to a much lower than expected, eligible population rate of 2.66%.

Statistical interim analysis and early stopping rules

No statistical interim analyses were planned or done. Patient recruitment stops when a total number of 130 patients have been included and finished their intervention or when the deadline August 31, 2022 is reached.

Timing of final analysis

The final analysis for the between group comparison (*Intervention group vs. Control comparator group*) for the primary endpoint (baseline, 4-, 8- and 12-weeks follow-up) is planned to be performed after the last randomised patient has completed the 12 weeks follow-up. The publication of the trial will be prepared when the data have been received and cleaned (anticipated by April 2023).

Timing of outcome assessments

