Women who have participated in a parallel performed nationwide cross-sectional survey study and reported shoulder pain or impairment as their primary discomfort after BCS or mastectomy combined with either SLND or ALND due to breast cancer, and fulfilling the following inclusion and exclusion criteria are considered eligible for the randomised trial:

Inclusion criteria

1. Breast cancer patients who underwent unilateral BCS or mastectomy on the left or right side, including SLND or +/- ALND within the last 3-7 years (2015-2019)
2. Currently living in the Region of Southern Denmark or Central Denmark Region with a radius of 75 km from Vejle Hospital
3. Between 18 and 71 age at the time of surgery for primary breast cancer
4. Indicate pain in chest and/or shoulder area (shoulder impairments) as the biggest problem/late-term effect in everyday life
5. Indicate impaired shoulder function due to pain or due to tightness/tension
6. Indicate shoulder pain at rest, during general activities, during sleep or during flexion, rotation or abduction of the shoulder
7. A score ≥ 15 on the Disabilities of the Arm, Shoulder and Hand (Quick DASH) (9,10)
8. Agree to participate in this trial and sign written informed consent.

Exclusion criteria

1. No previous breast cancer (before 2014)
2. Cancer relapse after the date of index surgery, cancer spread outside of thorax and axilla, tumour fixed to chest wall
3. Primary- or secondary breast reconstruction performed at any time
4. Severe lymphedema (an average score $\geq 70\%$ in the first 7 questionnaires on the LYMPH-ICF-DK (11,12))
5. Bilateral breast cancer surgery
6. Previous surgery in the affected shoulder (prior to inclusion)
7. Previous shoulder or upper limb fractures (left/right)
8. Currently receiving chemo, immuno- or radiotherapy
9. Co-morbidity expected to influence shoulder function (e.g. rheumatoid arthritis, previous stroke, multiple sclerosis)
10. Other reasons for exclusion (e.g. pregnancy, not legally competent, unable to comprehend the information or unable to consent)

Recruitment

The CONSORT Flow Diagram will comprise number of patients screened, excluded (with reasons), randomised, stratified, receiving their allocated treatment, withdrawals (with reasons), and lost to follow-up (with reasons) and included in ITT analysis. The anticipated CONSORT Flow Diagram is depicted in [Figure 1](#).

Withdrawal/follow-up

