The reason for each crossover or withdrawal will be registered. Participants performing a crossover will remain in the study and be analysed following the intention-to-treat principle (i.e., remaining in their original group). The level of consent withdrawal will be classified as:

1. consent to continue follow-up and data collection;
2. consent to continue data collection only; or
3. complete withdrawal with no further follow-up and data collection (13).

In the CONSORT Flow Diagram numbers and reasons for withdrawal and/or loss to follow-up will be presented given at the 4-, 8- and 12-weeks (primary end point) outcome assessment; separately for the two intervention groups.

Baseline characteristics

The following data will be used to describe patients by randomisation group at baseline: mean age, height, weight, body mass index (BMI), smoking, alcohol consumption, highest education level, employment, index shoulder, dominant side affected, duration of shoulder symptoms, pain medication consumption due to shoulder related pain, depression, anxiety and outcome measures will be collected at baseline. The baseline characteristics are illustrated in [Table 1](#).

Categorical variables will be calculated and presented in numbers and percentages. While Means and Standard Deviations (SDs) will be calculated and presented for continuous variables if data follows a normal distribution; in case, continuous variables does not appear to follow normal distribution, median and interquartile range will be calculated. No tests of statistical significance will be conducted for baseline characteristics.

ANALYSIS

Primary outcome

Shoulder Pain and Disability Index (SPADI) [Time Frame: 0, 4, 8 and 12 weeks]

The primary outcome measure will be the between-group difference in change in SPADI-score ($\Delta\text{SPADI}_{12} = \text{SPADI}_{12\text{-weeks follow-up}} - \text{SPADI}_{\text{baseline}}$) from baseline to 12 weeks after initiating the treatment. SPADI is considered a valid, reliable, and responsive patient-reported questionnaire assessing shoulder pain and function, where each domain score is equally weighted and added to a total percentage score that ranges from 0 (best) to 100 (worst) (9,14) ([Figure 2](#)).

Key secondary outcomes

- *SPADI pain [Time Frame: 0, 4, 8 and 12 weeks]*

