outcome, a 95% CI excluding differences greater than 4 SPADI points between groups will be interpreted as indicating absence of a clinically meaningful difference. Dichotomous outcome variables will be analysed with logistic regression, with identical fixed effect factors and covariates as the mixed linear model described above. Missing data for dichotomous outcomes will be computed based on conservative (non-responder) imputations.

Subgroup analyses (24) will be used to examine whether the observed overall treatment effect varies across participants subgroups, and to whether the effect is modified by the value of a variable assessed at baseline, analysed by the following thresholds: median age, median duration of shoulder symptoms, obesity ($BMI \geq 30 \text{ kg/m}^2$), dominant side affected (left vs right). This statistical approach to evaluate potential effect modifiers, will be a test for statistical interaction whether the treatment effect (net benefit on change in the SPADI score) varies across levels of the effect modifier (25).

Missing data and sensitivity analyses

To handle missing data, repeated-measures linear mixed effects models will be used (26-29). These models are considered valid if data are “*Missing at Random*” (i.e., any systematic difference between the missing values and the observed values can be explained by differences in observed data) (30).

The following four strategies for handling and interpretation of missing data will be applied in the sensitivity analysis:

1. We will attempt to follow up all randomised participants, even if they withdraw from allocated treatment (i.e., contact all individuals unless they explicitly stated that they had withdrawn their consent);
2. Perform a main analysis of all observed data that are valid under a plausible assumption about the missing data (i.e., data as randomised; using linear mixed effects models, assuming that data are “*Missing at Random*”);
3. Perform sensitivity analyses to explore the effect of departures from the assumption made in the main analysis (i.e., non-responder-imputation: using the value at baseline to replace missing data);

these models will be informative about the robustness in case data are “*Missing Not At Random*”); and

4. Account for all randomised participants, at least in the sensitivity analyses (including strategy 2 and 3, plus the corresponding analyses based on the per protocol population) (28).

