31. Administration, U.S.F.D. What is a Serious Adverse Event? [Internet]. 2016 [cited 2019 26 Oct]. Available from: <https://www.fda.gov/safety/medwatch/howtoreport/ucm053087.html>

ANTICIPATED OUTLINE

[figure not shown]

Figure 1: CONSORT Flow Diagram of participants through the trial. Control comparator group (a minimal home-based program); Intervention group (individualised treatment).

THE FIGURE BELOW IS DEPICTED WITH ANTICIPATED CHANGES FROM BASELINE TO 12 WEEKS FOLLOW-UP!

[figure not shown]

Figure 2: Trajectory in SPADI-score in the *Control comparator group* (*a minimal home-based program*) and *Intervention group* (*individualised treatment*) at baseline, 4-, 8-, and 12 (primary end-point) weeks after initiating the treatment. Values are mean (95% CI).

Table 1. Baseline characteristics in the ITT population*

	Intervention Group (N =XX)	Control Comparator Group (N =XX)	Total Combined (N =XX)
General characteristics			
Mean age — years			
Height — cm			
Weight — kg			
Body Mass Index — kg/m ²			
Smoking Habits:			
Smoker— no. (%)			
Current smoker— no. (%)			
Not a smoker— no. (%)			
Highest Education level:			
Short — no. (%)			
Medium — no. (%)			
Long — no. (%)			
Employment:			
Employed for wages — no. (%)			
Self-employed — no. (%)			
Sick leave — no. (%)			
Retired — no. (%)			
Other — no. (%)			
Index shoulder:			
Right side — no. (%)			
Left side — no. (%)			
Dominant side affected:			
Right side — no. (%)			
Left side — no. (%)			
Duration of shoulder symptoms — years			
Outcome measures			
SPADI score† — 0 to 100			
Shoulder pain — 0 to 10			
Shoulder function — 0 to 10			
GPE impression of the treatment's success — 0 to 7			
A-ROM in the affected shoulder — degree			
P-ROM in the affected shoulder — degree			
NRS maximum shoulder pain intensity — 0 to 10			
NRS shoulder pain during general activities — 0 to 10			
NRS shoulder pain at rest — 0 to 10			
NRS shoulder pain during sleep — 0 to 10			
NRS shoulder pain assessment during flexion/rotation/abduction — 0 to 10			

* Plus-minus values are mean \pm SD unless otherwise indicated

† The Shoulder Pain and Disability Index (SPADI) ranges from 0 (best) to 100 (worst), with lower scores indicating better disease status.

Table 2: Primary and Key Secondary Outcomes at 12 weeks in the ITT population*

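### The subgroup modifier for dominant side is given the levels left and right, which do not define whether the affected shoulder is on the dominant side

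*SAP*

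**What the plan says.** The subgroup paragraph under Analysis methods asks "whether the effect is modified by the value of a variable assessed at baseline" and names four modifiers: age and symptom duration, each split at the median, obesity, and "dominant side affected (left vs right". Each is to be examined with an interaction test of whether the treatment effect on SPADI change "varies across levels of the effect modifier". The levels written beside a modifier therefore fix the contrast that is tested.

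The Baseline characteristics section lists "index shoulder, dominant side affected" as two separate items. Table 1 shows both, one above the other, and gives each the rows right side and left side. Under the inclusion criteria, women "underwent unilateral BCS or mastectomy on the left or right side", so each has one affected side, and whether it is her dominant side has a definite answer once her handedness is known.

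Nowhere does the SAP give a yes/no level for this variable, or a rule that derives it from index shoulder and handedness.

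**The concern.** The variable is named for one attribute and coded with the levels of another. The clinical question that the name implies is whether treatment works differently when the arm a woman mainly uses is the affected one. That needs a comparison of women affected on the dominant side with women affected on the other side. Left against right does not make that split.

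An analyst who follows the text must either run a contrast other than the one named or depart from the pre-specified levels. In the first case, a finding about body side or handedness could be read as evidence about dominance. In the second, the coding is settled at the analysis stage, possibly with results in view, and the test loses the protection of having been specified in advance.

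**Working it through.** **1. The levels against the name.** Three readings of left vs right are possible.

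| Reading | What is compared | Contrasts dominant-affected with non-dominant-affected? |
|---|---|---|
| (a) side of the affected shoulder | left-affected vs right-affected women; same as index shoulder | Only indirectly, as a proxy |
| (b) which side is dominant | left-handed vs right-handed women | No |
| (c) side, among women affected on the dominant side | left vs right within that group | No; the comparison group is left out |

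**2. Inputs for size.** From the SAP's sample size section: SD 15.41, n=130 (about 65 per group), two-sided alpha 0.05, relevant difference 8 points. Assumed, because the SAP gives no figure: left-handed fraction q of 5–15%; affected side split 50/50 and independent of handedness; four equal cells; a true dominance interaction of 8 points.

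The SAP states no figure for this subgroup test, so there is none to reproduce. As a check on the inputs, the main comparison with 65 per group has SE = 15.41 × √(2/65) = 2.70 and power Φ(8/2.70 − 1.96) = 84.1%. This is close to the stated 85%; the small gap is not part of this point.

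**3. Reading (a), dilution.** Among women affected on the right, a fraction 1 − q are affected on the dominant side; among those affected on the left, a fraction q. If the treatment effect is τ₁ when the dominant side is affected and τ₀ when it is not, then

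- effect in right-affected women = (1 − q)τ₁ + qτ₀
- effect in left-affected women = qτ₁ + (1 − q)τ₀
- difference = (1 − 2q)(τ₁ − τ₀)

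The left/right interaction is thus the dominance interaction multiplied by 1 − 2q.

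**4. Reading (a), power.** With N/4 = 32.5 women per cell, SE = 15.41 × √(4/32.5) = 5.41. Power = Φ(d/SE − 1.96) + Φ(−d/SE − 1.96), with d = 8(1 − 2q).

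| Coding | Factor | d (points) | Power |
|---|---|---|---|
| Yes/no dominance | 1.00 | 8.0 | 31.6% |
| Left/right, q = 5% | 0.90 | 7.2 | 26.5% |
| Left/right, q = 10% | 0.80 | 6.4 | 22.0% |
| Left/right, q = 15% | 0.70 | 5.6 | 17.9% |

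**5. Reading (b), size of the left level.** 130 × 0.05 = 6.5 and 130 × 0.15 = 19.5, so about 7–20 women. Nobody is dropped.

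**6. Reading (c), size of the left level.** Half of the women, 65, are affected on the non-dominant side and drop out. The left level holds 130 × 0.5 × 0.05 = 3.25 to 130 × 0.5 × 0.15 = 9.75, so about 3–10 women.

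**The case against.** The best defence is that this is an ambiguous label rather than a settled plan to test body side. Because index shoulder and "Dominant side affected" are listed separately at baseline, the second may record which side is dominant, and the yes/no modifier could then be derived by comparing the two. That is plausible and is why the fix is cheap. But the SAP does not state the derivation, and the levels it does state are not those of the derived variable.

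Table 1 can also be called weak support. It is an unfilled shell with other loose labels: smoker appears beside current smoker, and the global perceived effect is listed at baseline although it is collected only at follow-up. On its own Table 1 would prove little. Here it agrees with the levels in the subgroup paragraph, which is the text that governs the test.

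The impact is small as well: one subgroup test, outside the primary analysis and the ordered key secondary outcomes, and no table shell for subgroup results. This stands in full.

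Two stronger readings are tempting. A reader might infer that the test cannot address dominance at all. Under reading (a) that goes too far, because affected side keeps 0.90–0.70 of a true interaction under the assumptions above. A reader might also measure the loss from a conventional 80% power. No subgroup test here has that: the sample size was set for the main comparison, and even perfect coding gives about 32% for an 8-point interaction. The SAP's correction to its recruitment estimate reports far fewer eligible and willing women than expected, so actual power may be lower still. Recoding makes the test ask the right question; it does not make it a strong test.

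**Conclusion.** The point holds as a wrongly defined modifier. None of the three readings of left vs right directly contrasts women affected on the dominant side with women affected on the other side. The nearest, affected side, repeats index shoulder and misclassifies 5–15% of women if that share is left-handed. The other two readings leave a small left level and answer different questions.

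That the left and right levels do not fit the variable's name follows from the text alone. The sizes rest on the assumed handedness range, a balanced affected side independent of handedness, equal cells, the planning SD and the planned n. The document does not show which of the three contrasts would actually be run, so it does not support saying that the plan is to test laterality. No primary or key secondary estimate, error rate or sample size changes.

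**What to change.** Before the subgroup analysis is run, replace the levels in the subgroup paragraph with: affected shoulder on the dominant side, yes or no, where yes means that the index shoulder is on the same side as hand dominance. Test the group by yes/no interaction on SPADI change. Change the corresponding Table 1 rows to yes and no, and keep right and left for index shoulder only.

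The cost is one line of SAP text, one table edit and one derived variable. No new data are needed provided hand dominance was recorded at baseline. The variable's name implies this, but the SAP does not confirm it. If it was not recorded, the subgroup should be renamed for what it measures (side of the affected shoulder) and not reported as dominance.

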Thus, the following sensitivity analyses will be performed on various population analyses, including a non-responder imputation and per-protocol, to examine the robustness by revealed similar results in these sensitivity analyses. Robustness is a concept that refers to the sensitivity of the overall conclusions to various limitations of the data, assumptions, and analytic approaches to data analysis. Robustness implies that the treatment effect and primary conclusions of the trial are not substantially affected when analyses are carried out based on alternative assumptions or analytic approaches.

Additional analyse

No additional analyses on the primary and key secondary outcomes are planned from baseline to 12 weeks follow-up.

Harms

Serious adverse events (SAE) will be categorised in accordance with the definitions established by the United States Food and Drug Administration (e.g. hospitalisation or death) (31). All categorical types of SAE's will be presented for each group and statistical tested by using logistic regression. The SAEs will be presented as illustrated in **Table 3**.

Statistical software

All data analysis will follow the statistical methods described above, and will be performed applying STATA (Statacorp, College Station, Texas, USA) and SAS (SAS Institute Inc., Cary, North Carolina, USA) software.

REFERENCES

1. American Cancer Society. Breast Cancer Facts & Figures 2019-2020 [Internet]. 2020 [cited 2022 Aug 08, pp. 4]. Available from: <https://www.cancer.org/content/dam/cancer-org/research/cancer-facts-and-statistics/breast-cancer-facts-and-figures/breast-cancer-facts-and-figures-2019-2020.pdf>
3. World Medical Association (WMA). WMA Declaration of Helsinki – Ethical Principles for Medical Research Involving Human Subjects [Internet]. 1964 [cited 2018 Aug 14]. Available from: <https://www.wma.net/policies-post/wma-declaration-of-helsinki-ethical-principles-for-medical-research-involving-human-subjects>

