Outcome	12 weeks after initiating the treatment		Between-Group Difference in Mean Improvement	
	Intervention Group	Control Comparator Group	Difference in LSMeans (95%CI)	P-Value
	Mean	SE	Mean	SE
Primary endpoint				
Change SPADI score — 0 to 100				
Key secondary outcome measures				
Change SPADI pain (0-10)				
Change SPADI function (0-10)				
Change Clinical response (SPADI change score)				
GPE impression of the treatment success (0-7)				
Change A-ROM in the affected shoulder (degree)				
Change P-ROM in the affected shoulder (degree)				
Number of treatments received due to shoulder symptoms (mean)				
NRS maximum shoulder pain intensity (0-10)				
NRS shoulder pain during general activities (0-10)				
NRS shoulder pain at rest (0-10)				
NRS shoulder pain during sleep (0-10)				
NRS shoulder pain assessment during flexion/rotation/abduction (0-10)				
Response to Treatment				
SPADI minimal important change criteria† no. (%)				

* All analyses will be based on the Intention-To-Treat (ITT) population: Using Repeated-Measures, Mixed Models (with no simple imputation for missing data); Estimates will be least squares means (LSMeans) and Standard Errors (SE) with the difference between groups reported with 95% Confidence Intervals (CI).

† Patients will be classified as having a clinically relevant change if the SPADI score improves by 8 points or more; missing data will be replaced by single-step non responder imputation.

Table 3: Serious Adverse Events at 12 weeks in the ITT population*

	Intervention Group	Control Comparator Group
Serious Adverse Event (SAE) - no (%)		
Musculoskeletal		
Deep infection, no. (%)		
Shoulder dislocation, no. (%)		
Shoulder fracture, no. (%)		
Cardiovascular		
Vascular injury (arterial and venous damage), no. (%)		
Pulmonary embolism, no. (%)		
Deep venous thrombosis, no. (%)		
Acute myocardial infarction, no. (%)		
Nervous system		
Nerve injury, no. (%)		
Deaths, no. (%)		
Discontinuation due to AE(s) — no. (%)		

* This table includes all Serious Adverse Events (SAE's) that occurred during the 12 weeks study period, but not necessarily a causal relationship with the treatment administered. An adverse event was classified as serious if it was fatal or life-threatening, required or prolonged inpatient hospitalisation, was disabling, resulted in (a congenital anomaly or birth defect), or required medical or surgical intervention to prevent permanent impairment or damage.

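### Every SAE type is to be tested by ordinary logistic regression with no test statistic named and no rule for zero cells, yet at 65 women per arm a type with a risk up to about 1% will usually have events in one arm only or in neither

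*SAP*

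**What the plan says.** The Harms section of the SAP states that the categorical types of SAE "will be presented for each group and statistical tested by using logistic regression". It adds: "The SAEs will be presented as illustrated in" Table 3.

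That table, headed "Table 3: Serious Adverse Events at 12 weeks in the ITT population", has an overall row, "Serious Adverse Event (SAE) - no", nine specific types (deep infection, dislocation, fracture, vascular injury, pulmonary embolism, deep venous thrombosis, myocardial infarction, nerve injury and death) and a row for discontinuation due to adverse events. As it appears, it has two group columns and no column for an effect estimate or p-value. Table 2, for the efficacy outcomes, has both.

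The section on sample size plans about "65 participants in each group". The observation window in the Table 3 footnote is the 12-week study period. Nowhere does the SAP give an expected SAE rate, a minimum count for testing, a choice between Wald, score and likelihood-ratio tests, or an exact or penalised alternative.

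**The concern.** Maximum-likelihood logistic regression gives a finite group odds ratio only if both arms have at least one event (and one non-event, which is not in question here). The listed types are rare, the arms are small and the follow-up is short, so many types can be expected to have an empty cell.

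With events in one arm only, the estimate runs off to infinity or zero. What is then printed as a p-value depends on the test: the Wald version is uninformative, while the likelihood-ratio version is not. With no events in either arm there is nothing to estimate. The plan names two packages, STATA and SAS, and no test, so the reported p-value is not fixed in advance. What is at stake is a harms p-value that either cannot signal an imbalance or depends on a choice made after the data are seen.

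**Working it through.** **Inputs.** n = 65 per arm (SAP, sample size section). The plan gives no SAE risk and so no harms figure to reproduce. The risk per type, p, is an assumption, equal in both arms, shown over 0.1% to 2%.

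**Step 1: how often cells are empty.** Let q = (1 − p)^65 be the chance of no event in one arm. Then one arm only = 2q(1 − q), neither arm = q², both arms = (1 − q)².

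| Assumed risk | q | One arm only | Neither arm | Both arms |
|---|---|---|---|---|
| 0.1% | 0.937 | 11.8% | 87.8% | 0.4% |
| 0.5% | 0.722 | 40.1% | 52.1% | 7.7% |
| 1% | 0.520 | 49.9% | 27.1% | 23.0% |
| 2% | 0.269 | 39.3% | 7.2% | 53.4% |

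A finite odds ratio needs the last column.

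**Step 2: what the tests give at 3 vs 0** (model with group only).

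- Likelihood ratio: separate arms, 3 ln(3/65) + 62 ln(62/65) = −12.157; pooled, 3 ln(3/130) + 127 ln(127/130) = −14.272. Twice the difference is 4.23 on 1 df, p = 0.040.
- Score: z = (3/65) / √[(3/130)(127/130)(2/65)] = 1.75, p = 0.080.
- Fisher, for comparison: 2 × C(65,3)/C(130,3) = 2 × 43,680/357,760 = 0.244.
- Wald: each further iteration moves the log odds of the empty arm by about one unit, while its standard error grows by a factor of about e^0.5 = 1.65. The ratio shrinks towards zero. After 15 or more iterations p is 0.96 to 1.00. The same happens at 6 vs 0 and 10 vs 0, so a larger imbalance does not help.

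**Step 3: how often the choice of test changes significance.** At 1 vs 0 and 2 vs 0 no version is below 0.05 (likelihood ratio 0.24 and 0.094; score 0.32 and 0.15). Wald and likelihood ratio part company from 3 vs 0. The chance of 0 against 3 or more is 2q × P(X ≥ 3), with X binomial(65, p): 0.008%/0.6%/2.9%/7.6% per type.

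**Step 4: one comparison for any SAE.** If the nine types are independent and equally likely, the risk of at least one SAE is 1 − (1 − p)^9 = 0.9%/4.4%/8.6%/16.6%. Events in both arms then have probability 20%/90%/99%/over 99.9%.

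**The case against.** - **The SAP promises a test and no odds ratio.** This stands. A reader might infer from the last column of Step 1 that the planned test fails that often. It does not: likelihood-ratio and score tests of the same model exist whenever either arm has an event. What fails is the Wald test and any reported odds ratio.
- **The problem depends on assumed rates.** This also stands. It would be tempting to say that most types will give no odds ratio whatever the rate. At 2% a finite odds ratio is slightly more likely than not (53%), so the statement holds only up to about 1%.
- **The choice of test seldom matters for a given type.** Correct: at most 7.6% over the range (Step 3). Nor is a general excess of false positives supported. The exact type I error of the likelihood-ratio test is 0.01%/0.6%/2.9%/7.7% and passes 5% only above a risk of about 1.4%.
- **The model and the categories are not certain.** The Harms text first refers to regulatory seriousness definitions, so its types could be those categories and not the nine rows of Table 3. The general rule for dichotomous outcomes under Analysis methods would add stratification factors. Step 2 uses group alone, so its p-values would change, but added strata would make cells sparser and not fuller.
- **Recruitment.** The correction in the sample size section reports 31 willing women in one region, "corresponding to a much lower than expected, eligible population rate of 2.66" per cent. A reader might infer a trial of that size. The eligibility criteria also admit women from a second region, and the final number is not given, so the figures here use the planned 65.

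**Conclusion.** The concern holds as a minor one. The plan commits each SAE type to a method that, at the planned size and at risks up to about 1%, is unlikely to give a usable Wald test or odds ratio, and it does not say which test is meant or what happens when a cell is empty. The probability of an empty cell in at least one arm is 99.6%/92%/77%/47% over the assumed risks (100% minus the last column of Step 1). A change in significance through the choice of test is uncommon.

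The damage stops at the harms p-values and statements based on them. SAEs are not among the key secondary outcomes tested in order, and counts per group are to be shown in any case. The result rests on equal risks in both arms, risks chosen for illustration and full recruitment. The mechanism itself, an infinite estimate with a Wald p-value near 1, needs none of these.

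**What to change.** Replace the testing sentence in the Harms section with wording such as:

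> *The number of women with at least one SAE will be compared between groups by an exact unconditional test based on the score statistic, with the 95% CI for the risk difference obtained by inverting the same test. Single SAE types will be listed per group as in Table 3, without testing.*

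This interval exists at zero counts: 3 vs 0 gives 4.6 percentage points (−1.2 to 13.1), and 0 vs 0 gives about −6 to 6.

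The p-value and interval must come from one method. Fisher's p beside an unconditional score interval can contradict it: at 4 vs 0 Fisher gives 0.119 and the unconditional test 0.046; at 5 vs 0, 0.058 and 0.028.

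If tests per type are kept, use one of these:
- Fisher's exact test, not paired with an interval from another method; or
- Firth-penalised logistic regression with its profile-likelihood interval and penalised likelihood-ratio p-value (3 vs 0: odds ratio 7.3, 0.7 to 994, p = 0.107).

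Define the Table 3 row "Serious Adverse Event (SAE) - no" (%) as women with any SAE, and add the p-value and interval to that row.

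The cost is two sentences and two table cells, with no effect on trial conduct or on the efficacy analyses. The drawbacks are that there is no adjustment for strata and that power stays low at these counts, so the interval should carry the interpretation. At moderate any-SAE rates logistic regression would usually also run on that row (Step 4); the exact method is preferred because it does not depend on that.
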